#### **9.4 Pharmacodynamics: Cytokines**

**9.4.1 Collection of Samples:** For patients treated on Arm A (patients who receive lenalidomide beginning Cycle 1), collection of blood samples will occur on Days 1 (baseline), 3 and 8 of the Cycle 1 and Day 1 of Cycles 2, 3, 5, 7 and every 6 months subsequently. For patients treated on Arm B (patients who receive lenalidomide beginning with Cycle 4) samples will be collected at Day 1 of Cycle 1 (baseline), Day 1 of Cycles 4, 5, 7 and every 6 months subsequently.

**9.4.2 Handling of Samples:**

Venous whole blood (approximately 10 mL) should be drawn into two 5-mL potassium EDTA (lavender-top) vacutainers. Samples will then be spun at 1,200 x g for 10 minutes to isolate plasma. Plasma in three separate vials will be stored in -80°C freezer. Each sample will be labeled with the protocol number, patient number, reference time point relative to the protocol, date and time the sample was obtained, and date and time the sample was placed in the -80°C freezer until further analysis.

**9.4.3 Sample and Data Analysis:**

The samples will be analyzed in batches to assess cytokine (such as IL-6, TNF- $\alpha$ , VEGF, bFGF) and soluble chemokines will be examined by a multiplex flow cytometry assay or ELISA. Other cytokines, chemokines, or soluble factors may be assessed on residual material not used for these studies. These studies will be done in the CLL experimental Therapeutics Laboratory

#### **9.5 Flow Cytometry B-, T-, and NK-cell subsets and activation status**

These studies will be performed at the OSU CLL Experimental Therapeutics Laboratory.

#### 9.5.1 **Collection of Specimens**

For patients treated on Arm A (patients who receive lenalidomide beginning Cycle 1), collection of blood samples will occur on Days 1 (baseline), 3 and 8 of the Cycle 1 and Day 1 of Cycles 3, 5, 7 and every 6 months subsequently. For patients treated on Arm B (patients who receive lenalidomide beginning with Cycle 4) samples will be collected at Day 1 of Cycle 1 (baseline), Day 1, 3, and 8 of Cycle 4, Day 1 of Cycle 5, 7, and every 6 months subsequently.

#### 9.5.2 **Handling of Specimens**

One x 5mL of blood will be collected in sodium heparin containing green top tube (Flow cytometry). Each sample will be labeled with the protocol number, patient number, reference time point relative to the protocol, date and time the sample was obtained. The heparin green top tube will be transported at room temperature to the flow cytometry laboratory.

#### 9.5.3 **Sample and Data Analysis.**

Changes in subsets and activation status of B-, T-, and NK lymphocytes in peripheral blood following lenalidomide therapy will be evaluated using multiparametric flow cytometry immune modulation panel at OSU. Lymphocyte CD4, CD8, T-regulatory, and NK cell subsets will be enumerated and markers of activation status will be characterized for each.

**CLL cell activation studies:** B-cell activation will be further characterized by upregulation of CD154 as the primary measure (based upon our data), along with CD40, CD80, CD69, and CD86 by flow cytometry. Additionally, we will measure serial changes in IL-21 receptor expression on CLL cells which we recently have shown is up-regulated by lenalidomide. Change in CD154 expression will be correlated with pharmacokinetics, immune, and clinical response.

### 9.6 **Pharmacodynamic Studies: T-cell Function and Epigenetic Changes in CLL Cells**

#### 9.6.1 **Collection of Specimens**

For patients treated on Arm A (patients who receive lenalidomide beginning Cycle 1), collection of blood samples will occur on Days 1 (baseline), 3 and 8 of the Cycle 1 and Day 1 of Cycles 2, 3, 5, 7 and every 6 months subsequently. For patients treated on Arm B (patients who receive lenalidomide beginning with Cycle 4) samples will be collected at Day 1 of cycle 1 (baseline), Day 1, 3, and 8 of cycle 4, Day 1 of cycle 5, 6, 7, and every 6 months subsequently.

#### 9.6.2 **Handling of Specimens**

Two x 10mL of blood will be collected in sodium heparin containing green top tube (Flow cytometry). Each sample will be labeled with the protocol number, patient number, reference time point relative to the protocol, date and time the sample was obtained.

### 9.6.3 Sample and Data Analysis.

**T-cell Functional activation studies:** CRM197 specific T cells numbers and frequency will be evaluated by flow cytometry. CD4 cell production of specific cytokines will be assessed. Other T-cell dependent activation studies toward primary tumor cells will be performed including ELISPOT and T-cell synapse studies as previously reported. These will be done in the CLL experimental Therapeutics Laboratory.

**Activation and Epigenetic Changes in CLL Cells:** Activation and epigenetic studies will be performed in the OSU CLL Experimental Therapeutics Laboratory. Tumor cells will be isolated from peripheral blood by ficoll density gradient centrifugation using Rosette-Sep reagent (Stem Cell Technologies, Vancouver BC). Cells will be washed and counted, and histones acid-extracted from  $5 \times 10^7$  cells as we described previously.[68] Histones will be analyzed by mass spectrometry according to our published procedures [69] Activation studies will be performed using methods previously published by our group.[70] Other studies related to understanding mechanism of action of lenalidomide, CLL biology, or predicting response to lenalidomide may be performed on remaining material.

### 9.7 Correlative Studies Prioritization

Studies [9.1-9.4](#) rely upon serum or plasma for their analyses. Adequate sample volume has been requested to perform the studies outlined. Studies [9.5](#) and [9.6](#) rely upon adequate tumor and immune cell subsets. Priority will be given to the immune subset analysis by flow cytometry; next activation studies, then T cell function, and epigenetics changes based upon the number of CLL cells available at each sample time point.

## 10. STUDY CALENDAR

Screening evaluations including history and physical examination and all laboratory studies are to be conducted within 14 days prior to the start of protocol therapy. CT scans of the chest, abdomen and pelvis will be completed within 6 weeks and bone marrow biopsy and aspirate (optional) are to be completed within 12 weeks prior to the start of therapy and should include evaluation for myelodysplasia. Visits Cycle 7+ have a +/- 7 day visit window. Follow-Up visits have a +/- 14 day visit window. Additional required data are summarized in the study calendar.

**Schedule of Study Assessments: Arm A (Concurrent)**

Procedure	Screening	Cycle 1 & 2				Cycle 3	Cycle 4	Cycle 5	Cycle 6	Cycle 7+	End of Therapy o	Follow-Up p
		W1	W2	W3	W4							
Clinical Assessment												
Informed Consent	X											
Physical Examination a	X	X	X	X	X	X	X	X	X	X	X	X
ECOG Performance Status b	X	X	X	X	X	X	X	X	X	X	X	X
Concomitant medications	X	X	X	X	X	X	X	X	X	X	X	X
Interval infection history c		X	X	X	X	X	X	X	X	X	X	X
Record adverse events		X	X	X	X	X	X	X	X	X	X	
Perform Drug Accountability d	X	X	X	X	X	X	X	X	X	X		
Education and Counseling e		X				X	X	X	X	X		
Response assessment n						X		X		X n	X	X
Laboaratory Studies and Procedures												
ECG	X											
Complete blood count m	X	X	X	X	X	X	X	X	X	X	X	X
Serum chemistries f	X	X	X	X	X	X	X	X	X	X		X
Urinalysis	X											
Quantitative serum immunoglobulins	X					X		X		Every 6 mo	X q	X
Direct and indirect antiglobulin test	X											
TSH	X											X
Pregnancy testing g	X	X	X	X	X	X	X	X	X	X	X	
Bone marrow biopsy h	Optional											X
Risk stratification studies i	X											
CT scans r	X											
Anti-pneumococcal antibody titers		X				X		X	X			
Treatment												
Allopurinol l		X	X	X	X							
Thromboprophylaxis k		X	X	X	X	X	X	X	X	X		
Dispense Lenalidomide l		X				X	X	X	X	X		
Lenalidomide		X	X	X	X	X	X	X	X	X		
PCV13 administration						X		X				
Correlative Studies												
Pharmacokinetic Studies s			C2 D1,2									
Pharmacodynamic Studies t	X	C1 D1,3 C2 D1	C1 D8			X		X				

### Schedule of Study Assessments: Arm B (Sequential)

Procedure	Screening	Cycle 1	Cycle 2	Cycle 3	Cycle 4 & 5				Cycle 6	Cycle 7+	End of Therapy o	Follow-Up p
					W1	W2	W3	W4				
Clinical Assessment												
Informed Consent	X											
Physical Examination a	X	X	X	X	X	X	X	X	X	X	X	
ECOG Performance Status b	X	X	X	X	X	X	X	X	X	X	X	
Concomitant medications	X	X	X	X	X	X	X	X	X	X	X	
Interval infection history c		X	X	X	X	X	X	X	X	X	X	
Record adverse events		X	X	X	X	X	X	X	X	X	X	
Perform Drug Accountability d	X				X	X	X	X	X	X	X	
Education and Counseling e					X				X	X	X	
Response assessment n					C5					X n	X	X
Laboaratory Studies and Procedures												
ECG	X											
Complete blood count m	X	X	X	X	X	X	X	X	X	X	X	X
Serum chemistries f	X	X	X	X	X	X	X	X	X	X	X	
Urinalysis	X											
Quantitative immunoglobulins	X	X		X	X					Every 6 mo	X g	X
Direct and indirect antiglobulin test	X											
TSH	X										X	
Pregnancy testing g	X				X g	X	X	X	X	X	X	
Bone marrow biopsy h	Optional										X	
Risk stratification studies i	X											
CT scans r	X										X	
Anti-pneumococcal antibody titers		X		X	X							
Treatment												
Allopurinol l					X	X	X	X				
Thromboprophylaxis k					X	X	X	X	X	X		
Dispense Lenalidomide l					X	X	X	X	X	X		
Lenalidomide					X	X	X	X	X	X		
PCV13 administration		X		X								
Correlative Studies												
Pharmacokinetic Studies s					C5 D1,2							
Pharmacodynamic Studies t	X	X			C4 D1,3 C5 D1	C4 D8			X			

- a. Physical examination should include vitals signs, weight, general physical examination (including neurologic examination), measurement of liver and spleen span in centimeters below the costal margin in the anterior axillary line, and bi-dimensional measurement of cervical, supraclavicular, axillary, and inguinal nodes.
- b. See [Appendix A](#).
- c. See [6.3.10](#) for required information to be documented for each episode of infection.
- d. Patient medication diary is reviewed to assess patient compliance on the first day of each cycle in which lenalidomide is administered.
- e. The Lenalidomide Education and Counseling Guidance Document ([Appendix D](#)) must be completed and signed by a trained counselor at the participating site prior to each dispensing of lenalidomide treatment. A copy of this document must be maintained in the patient records. The Lenalidomide Information Sheet ([Appendix E](#)) will be given to each patient receiving lenalidomide treatment. The patient must read this document prior to starting lenalidomide study treatment and each time they receive a new supply of study drug.
- f. Serum chemistries should include: comprehensive metabolic panel, phosphate, uric acid, and LDH.
- g. Pregnancy tests for females of childbearing potential. A female of childbearing potential (FCBP) is a sexually mature female who: 1) has not undergone a hysterectomy or bilateral oophorectomy; or 2) has not been naturally postmenopausal (amenorrhea following cancer therapy does not rule out childbearing potential) for at least 24 consecutive months (i.e., has had menses at any time in the preceding 24 consecutive months). Pregnancy tests must occur within 10 – 14 days and again within 24 hours prior to initiation of lenalidomide. FCBP with regular or no menstruation must have a pregnancy test weekly for the first 28 days and then every 28 days while on study treatment (including breaks in treatment); at discontinuation of lenalidomide and at Day 28 post the last dose of lenalidomide. Females with irregular menstruation must have a pregnancy test weekly for the first 28 days and then every 14 days while on study treatment (including breaks in treatment), at discontinuation of lenalidomide and at Day 14 and Day 28 post the last dose of lenalidomide (see [Appendix C: Risks of Fetal Exposure, Pregnancy Testing Guidelines and Acceptable Birth Control Methods](#)).
- h. Unilateral bone marrow biopsy and aspirate will be obtained at end of treatment. In addition to routine pathology, aspirate samples should be studied for, interphase cytogenetics, standard CLL FISH panel, CpG stimulated karyotype, and flow cytometry. If patients decline bone marrow biopsy at end of study, these same studies should be done on peripheral blood. If patients demonstrate anti-ROR1 antibody response, a research bone marrow aspirate may be done every 6 months to isolate normal B-cells for correlative studies.
- i. Risk stratification studies will include serum  $\beta$ 2-microglobulin in addition to tests performed on the screening bone marrow biopsy specimen: IgVH mutational analysis (unless already known), interphase cytogenetics, stimulated karyotype and standard CLL FISH panel.
- j. Allopurinol should be administered beginning 3 days before first lenalidomide administration and continued through the first cycle of lenalidomide treatment in its entirety. Allopurinol can be continued during subsequent cycles at the treating physician's discretion.
- k. Thromboprophylaxis should begin with lenalidomide in patients at high-risk for venous or arterial thromboembolism (see [5.2.3](#)).
- l. Only enough lenalidomide for 28 days or one cycle of study treatment (whichever is shorter) may be provided to the patient each cycle.
- m. CBC is checked on D1 and D8 during the first cycle of lenalidomide exposure and during the second cycle and/or any subsequent cycle in which the dose of lenalidomide has been escalated. CBC should be checked weekly during any subsequent cycle in which the dose of lenalidomide has been reduced for hematologic toxicity.
- n. Response is assessed clinically (CBC, physical examination) after every 2 cycles of lenalidomide treatment beginning with Cycle 3 (Arm A) or Cycle 5 (Arm B), respectively. For patients meeting clinical criteria for CR for  $\geq$  2 months, bone marrow biopsy and CT scans should be performed to confirm response.
- o. The End of Therapy visit is defined as that occurring after 24 cycles. Patients discontinuing treatment at other times secondary to toxicity, progression, or preference only need the clinical assessment (except informed consent and education and counseling) and a complete blood count. Patients discontinuing for any reason are followed for at least 30 days to ensure resolution of any adverse events; however, these patients will still be followed for outcome until meeting criteria outlined in footnote "p" below.
- p. Patients no longer receiving active treatment are followed every 3 months during the first year and every 6 months thereafter until the patient receives a new CLL therapy, withdrawal of consent, or death.
- q. Unless completed within the last month.
- r. CT scans of the chest, abdomen, and pelvis.

- s. For patients treated on **Arm A** (patients who will receive lenalidomide during cycles 1 and 2), pharmacokinetic assessments of lenalidomide will occur during days 1 and 2 of cycle 2. Samples will be collected at the following time points: prior to dosing (time 0), 0.5, 1, 2, 3, 4.5, and 6 hours after dose administration on day 1 of cycle 2. An additional sample will be obtained prior to lenalidomide ingestion on day 2 of cycle 2 (i.e. 24 hours after the dose is ingested on day 1). For patients in **Arm B** (patients who receive lenalidomide beginning in cycle 4) PK sampling will occur during days 1 and 2 of cycle 5. The sampling times will be consistent with those in Arm A and comprise the following time points: prior to dosing (time 0), 0.5, 1, 2, 3, 4.5, and 6 hours after dose administration on day 1 of cycle 5. An additional sample will be obtained prior to lenalidomide ingestion on day 2 of cycle 5 (i.e. 24 hours after the dose is ingested on day 1).
- t. Blood for pharmacodynamic studies is obtained on the first day of each cycle indicated unless stated otherwise. Details regarding specimen collection and handling are found in [Sections 9.1-9.6](#) above.

## 11. MEASUREMENT OF EFFECT

### 11.1 Response Criteria.

All patients will be evaluated for response. Response will be characterized according to the 2008 International Workshop on CLL (IWCLL) guidelines for the diagnosis and treatment of CLL, which include clinical, hematologic, and bone marrow features as outlined below.

### 11.2 Complete Response

Requires all of the following for a period of at least two months from completion of therapy:

- Absence of adenopathy on physical exam.
- No hepatomegaly or splenomegaly on physical exam.
- Absence of constitutional symptoms.
- Normal CBC as exhibited by polymorphonuclear leukocytes  $\geq 1500/\mu\text{L}$ , platelets  $> 100,000/\mu\text{L}$ , hemoglobin  $> 11.0 \text{ g/dL}$  (untransfused), and lymphocyte count  $< 5,000/\mu\text{L}$ .
- Bone marrow aspirate and biopsy must be normocellular for age with  $< 30\%$  of nucleated cells being lymphocytes. Lymphoid nodules must be absent. If the marrow is hypocellular, a repeat determination should be performed in one month.
- Patients who otherwise fulfill the criteria for CR after induction, with the exception of a persistent cytopenia that is believed to be treatment related, will be considered a partial response. Additionally, patients who fulfill the criteria for CR with exception of having bone marrow lymphoid nodules will be considered a partial response.
- Flow cytometry will be used to further characterize patients who achieve a CR by the above criteria. Those without evidence of marrow disease by this technique will be identified as such in analysis of treatment-free survival.

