### 5.3 Duration of Therapy

Patients demonstrating clinical benefit, defined as achievement of an objective response (CR, CRi, or PR) or stable disease (SD), may continue therapy for up to 24 cycles (approximately 2 years) of treatment with lenalidomide. Therapy beyond 24 cycles may be considered after discussion with the principal investigator and consultation with the study sponsor.

Investigators are encouraged to keep patients experiencing clinical benefit on study unless significant toxicity puts the subject at risk or routine noncompliance puts the study outcomes at risk. If the subject meets any 1 of the following criteria, withdrawal from treatment is mandatory:

- Disease progression meeting 2008 IWCLL consensus criteria for treatment.
- Intercurrent illness that prevents further lenalidomide administration.
- Any treatment-related Grade 4 non-hematologic toxicity.
- Unacceptable and/or unmanageable Grade  $\geq 3$  toxicity attributable to lenalidomide.
- Any treatment-related hematologic or non-hematologic toxicity delaying treatment more than 14 days.

- Development of autoimmune hemolytic anemia (AIHA) or immune-mediated thrombocytopenia (ITP)
- Subject elects to withdraw from study or becomes pregnant.
- General or specific changes in the patient's condition rendering the patient unacceptable for further treatment in the judgment of the investigator.
- Subject is noncompliant with study procedures and/or scheduled evaluations.
- Investigator considers withdrawal to be in the best interest of the subject.
- Diagnosis of new or secondary malignancies after initiating treatment

Subjects with inadequate study drug compliance (i.e.  $\leq$  80% of planned doses administered) may be replaced.

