### 11.3 Partial Response

Requires  $> 50\%$  decrease in peripheral lymphocyte count from pre-treatment value,  $> 50\%$  reduction in lymphadenopathy, and/or  $> 50\%$  reduction in Splenomegaly or hepatomegaly for a period of at least two months from completion of therapy. All lymph nodes will be measured bi-dimensionally and the sums of these added to determine if  $50\%$  or greater reduction has occurred. Patients may have bone marrow lymphoid nodules and persistent cytopenias. Additionally, these patients must have one of the following:

- Polymorphonuclear leukocytes  $\geq 1500/\mu\text{L}$  or 50% improvement from pre-treatment value.
- Platelets  $> 100,000/\mu\text{L}$  or 50% improvement from pre-treatment value.
- Hemoglobin  $> 11.0 \text{ g/dL}$  (untransfused) or 50% improvement from pre-treatment value.

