clinical efficacy using the two-year CR rate. Previous experience with lenalidomide suggests that late responses may be observed. Therefore, to effectively capture evidence of regimen efficacy (beyond the primary endpoint analysis) we will assess the CR rate in a pooled analysis across both arms since the main component of the regimen is lenalidomide therapy. If we find that one arm has shown to be superior to another in terms of antibody response rate as described above, then we will also compare the CR rates between these two arms in an exploratory manner. For the purposes of this trial, if a patient has a documented CR on at least two consecutive evaluations during the first two years, they will be deemed a clinical success. Given the extended time required to observe this clinical endpoint in these patients, we will use a one-stage design. With 44 patients, we will have at least 90% power and a Type I error of 0.10 to be able to detect a 25% or greater true CR rate versus the null hypothesis that the true CR rate is at most 10%. If 8 or more patients are deemed a clinical success as defined above, then we will consider this evidence of efficacy and worth pursuing further. Otherwise, if at most 7 of these 44 evaluable subjects have a CR at the end of two years of follow-up, then we will consider this insufficient clinical activity and may look to modify the treatment regimen to build on observed vaccine response.

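### The formal complete-response count in 13.3 relies on 11.2 criteria that must hold for two months after therapy ends, which does not fit an on-treatment two-year count; its stated 90% power is also slightly too high

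*Combined protocol and SAP*

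**What the plan says.** **The test.** Section 13.3 defines the patient-level event this way: "For the purposes of this trial, if a patient has a documented CR on at least two consecutive evaluations during the first two years". The cut-off follows: "If 8 or more patients are deemed a clinical success as defined above", the result is evidence of efficacy. The complementary sentence, introduced by the word *Otherwise*, reads "if at most 7 of these 44 evaluable subjects have a CR at the end of two years of follow-up". The null rate is at most 10% and the target is 25%. The stated properties are "With 44 patients, we will have at least 90% power and a Type I error of 0.10". Section 13.3 lists no CR criteria and does not cite section 11.

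**The criteria.** Section 11.1 applies the section 11 criteria to all patients. The CR entry, 11.2, opens "Requires all of the following for a period of at least two months from completion of therapy". The partial-response entry, 11.3, carries the same clause.

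**Response on treatment.** Section 5.3 says that patients with clinical benefit, "defined as achievement of an objective response (CR, CRi, or PR) or stable disease (SD), may continue therapy for up to 24 cycles", and allows longer treatment after consultation. Footnote n of the study calendar schedules a response assessment after every two cycles of lenalidomide. Once clinical CR criteria have been met for at least 2 months, "bone marrow biopsy and CT scans should be performed to confirm response".

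**The clock and the denominator.** The two years are years of lenalidomide in 1.2.1 and 13.5; 13.1 and 13.3 give no start. Section 13.3 keeps patients who drop out before the booster in the efficacy analyses as appropriate, and 13.6.2 puts all eligible patients in the main response analysis, with a possible exception for those who took no study medication. Section 13.4 allows up to 48 patients.

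**The concern.** The pooled CR rate is the only formal test of lenalidomide's clinical activity, and it is decided by a fixed count. The event being counted should therefore be unambiguous. As written, 13.3 counts CRs seen at consecutive visits within two years, while the criteria it must borrow ask for a hold that starts only when treatment stops. Treatment is planned to last about two years and may continue beyond that, so the two requirements barely overlap. Applied word for word, 11.2 would credit mainly responders who stopped early, which is not what the test is meant to measure.

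The operating characteristics matter for the same reason. A fixed cut-off has the stated error rates only at the stated sample size, and the text on who enters the efficacy analysis allows more than 44.

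**Working it through.** **1. Reproducing the stated rule.** Inputs from 13.3: n = 44, cut-off 8, null rate 0.10, target rate 0.25, one stage. With X binomial:

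- Type I error = P(X ≥ 8 | 44, 0.10) = 0.068, within the stated 0.10.
- Power = P(X ≥ 8 | 44, 0.25) = 0.892, just under the stated 90%.
- A cut-off of 7 gives alpha 0.146 and a cut-off of 9 gives power 0.806, so 8 is the right cut-off for n = 44.

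**2. Sample sizes that 13.3, 13.4 and 13.6.2 allow.**

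| n | cut-off | alpha | power |
|---|---|---|---|
| 44 | 8 | 0.068 | 0.892 |
| 45 | 8 | 0.076 | 0.906 |
| 46 | 8 | 0.084 | 0.918 |
| 47 | 8 | 0.093 | 0.929 |
| 48 | 8 | 0.102 | 0.939 |
| 48 | 9 | 0.046 | 0.881 |

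At n = 48 the printed cut-off passes the 0.10 limit, by 0.002.

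**3. Timing under the literal 11.2 clause.** Inputs: 28-day cycles and 24 cycles (schema and 5.3); follow-up at 30 ± 7 days and then every 3 months (5.4), with a ± 14 day window (section 10). Days run from first lenalidomide dose, without dose delays. Two months is taken as 56 to 61 days, 3 months as 91 days and two years as 730 days.

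- End of 24 cycles: 24 × 28 = day 672.
- Hold complete: 672 + 56 = 728 to 672 + 61 = 733.
- Safety visit: 672 + 30 ± 7 = day 695-709, too early to show a two-month hold.
- First 3-month visit: 672 + 91 ± 14 = day 749-777, after day 730.

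So in either arm no scheduled visit falls between the end of the hold and two years from first dose. Delays, or treatment beyond 24 cycles, push the hold later still.

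**4. Timing under footnote n.** Assessments every two cycles are 2 × 28 = 56 days apart. Two consecutive evaluations on treatment therefore already span about two months, without any reference to the end of therapy.

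**5. The start of the clock.** Arm B starts lenalidomide in Cycle 4, that is 3 × 28 = 84 days after Arm A. Counted from study entry, Arm B has 730 − 84 = 646 days from first dose by two years. That is 672 − 646 = 26 days short of 24 cycles, less than one cycle. Counted from first dose, the gap disappears.

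**6. Sensitivity, on assumed inputs.** The documents do not say what share of CRs a stricter reading would leave uncounted. If a share f is lost, power at n = 44 is P(X ≥ 8 | 44, 0.25(1 − f)): 0.80 for f = 10%, 0.68 for 20%, 0.51 for 30% and 0.18 for 50%. These values show how sensitive the rule is; they are not estimates. Under the literal clause the real loss would depend on how many responders stay on drug or complete the course.

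**The case against.** The strongest reply is that 13.3 sets its own rule for this trial, and that this rule with footnote n already describes an on-treatment CR held for about 56 days and confirmed by marrow and CT. Section 11.1 supplies the criteria without a cross-reference, and nothing shows that anyone would apply the completion-of-therapy clause to the formal count. Much of this stands: an on-treatment count is the likelier intention. But 13.3 does not set the clause aside, and 11.2 remains the only full definition.

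Three stronger readings are tempting, and the documents do not support them.

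- *The success and failure sentences of 13.3 contradict each other.* A reader might infer that a confirmed CR later lost counts in one and not in the other. The word *Otherwise* makes the second sentence most naturally the complement of the first. What is left is loose wording.
- *The missing start date disadvantages Arm B materially.* The effect is at most 26 days, and 1.2.1 and 13.5 already point to time on lenalidomide.
- *The test is badly underpowered.* The shortfall from 0.90 to 0.892 is at rounding level, and larger losses rest on assumed shares.

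It is also fair to say that the change comes late. Section 9 states that study endpoints have been met, so a new rule could be seen as chosen with data in hand. That is a reason to label it and to report both counts, rather than to leave the rule unstated.

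**Conclusion.** The point holds as a definitional conflict in a secondary endpoint, of minor to moderate weight. The 11.2 clause, taken literally, cannot credit a responder still on lenalidomide and leaves a 24-cycle completer no scheduled visit at which to qualify within two years of first dose. Sections 13.3 and 5.3 and footnote n assume the opposite. The timing result rests on 28-day cycles, no delays, and two months taken as 56 to 61 days.

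The stated power should read 0.892 with exact alpha 0.068. With all 48 patients in the analysis, a cut-off of 8 has alpha 0.102. Both departures are small.

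How many CRs are affected cannot be derived from the documents. It would be wrong to conclude that the CR result is invalid, or that the literal reading was used. The primary vaccine-response comparison does not depend on any of this.

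**What to change.** For the formal count, reconcile 11.2 with 13.3 and footnote n by adding to 13.3:

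- A clinical success is a CR meeting the 11.2 criteria at two consecutive scheduled evaluations, on or off lenalidomide, with the marrow and CT confirmation of footnote n. The completion-of-therapy clause does not govern this count.
- The two years run from first lenalidomide dose in both arms, in line with 1.2.1 and 13.5.
- The failure half reads as at most 7 clinical successes at n = 44 (in general, one fewer than the cut-off).
- Power at n = 44 is 0.89, with exact alpha 0.068.
- One analysis set is named that does not exclude patients differently by arm, for example all eligible randomized patients, with those who never start lenalidomide counted as non-successes. A set requiring any lenalidomide would drop every Arm B patient lost before the booster, because the booster is in Cycle 3 and the drug starts in Cycle 4, yet keep such patients in Arm A once they had started the drug.
- The cut-off is the smallest count with exact alpha at most 0.10 at the actual n: 8 for n = 44 to 47, 9 for n = 48.

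Label this a late clarification, and report the count under the literal 11.2 wording as a sensitivity result. This test needs no change to 11.3.

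The cost is some wording and one extra line in the report, with no new procedures. Stated power falls slightly below 90%: 0.892 at n = 44 and 0.881 at n = 48 with a cut-off of 9.
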